- Evaluation of quality of life in CML patients after imatinib discontinuation/resumption.
- Evaluation of progression/resistance in patients who relapse after imatinib discontinuation.

Endpoints:

Primary Endpoint:

- Negative Predicted Rate (NPV) of dPCR, i.e. the capability of the method to predict relapse-free patients.

Secondary Endpoints:

- Rate of dPCR positive relapse-free patients after 3 years follow up.
- Rate of relapse-free patients after 3 years follow up.
- Relapse free time.
- Quality of Life, as measured by EORTC-QLQ-T30 questionnaire.
- Rate of patients progressing or developing resistance after imatinib suspension.

Study Design and Methods:

In this study dPCR analysis will be performed on CML patients under imatinib therapy, with at least 18 months of consecutive negative standard Q-RT-PCR as performed in their own centers. The patients will sign an informed consent form (ICF), will subsequently be tested for dPCR and will stop imatinib. Then they will be monitored with standard Q-RT-PCR to assess the maintenance of the molecular remission. Collection of data will be prospective as each center will collect the data for 36 months. At the end of this period, a peripheral blood sample for dPCR analysis will be obtained from those patients who will still have undetectable BCR/ABL transcripts by Q-RT-PCR to verify CML eradication. Two years follow-up is then planned for patients maintaining CMR. During study, the patients with BCR/ABL transcripts detected by standard Q-RT-PCR will repeat the test not before 2 weeks and not after 2 months; in case of results confirmation and at least one BCR/ABL / BCR value >0.1%, the loss of the molecular remission will be declared and hematologic and bone marrow analyses will be performed. Such patients will immediately resume imatinib treatment at the same dosage used before interruption; progression of the disease will be evaluated as evolution to AP or BP and resistance to treatment will be defined as lack of complete hematological response at 3 months or of complete cytogenetic response at 6 months after resuming imatinib.

Patient's life quality during imatinib discontinuation/resumption will be evaluated through a Quality of Life (QoL) questionnaire until the end of this study (for patients maintaining molecular remission at baseline and at months 1, 6, 12, 24, 36, for relapsing patient at months 1, 6, 12 after imatinib resumption).

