The eligible patients will be entered between September 2011 and August 2012. Approximately 14 Centers will be involved in the study, including 5 international Centers.

Sample size

Sample size will be calculated so to provide with 80% power the alternative hypothesis that the Negative Predicted Value (NPV) of dPCR (i.e. the capability of the method to predict relapse-free patients) will exceed the one of traditional Q-RT-PCR, by more than 1.5.

$$H_0(N): rNPV \leq \delta$$

$$H_1(N): rNPV > \delta$$

where rNPV is the ratio of the Predicted Negative Values by the two tests respectively.

Promoter: University Milano-Bicocca

Product: Imatinib

With reference to the table below:

$$rNPV = \frac{NPV_{dPCR}}{NPV_{Q-RT-PCR}} = \frac{(n_{3+} n_4) / (n_{3+} n_4 + n_{6+} n_8)}{(n_{2+} n_4) / (n_{2+} n_4 + n_{6+} n_8)}$$

	Relapse Free 3 years since discontinuation			Relapsed within 3 years since discontinuation		
	Q-RT-PCR at entry			Q-RT-PCR at entry		
dPCR at entry	Positive	Negative	Total	Positive	Negative	Total
Positive	n ₁	n ₂	n ₁₊ n ₂	n ₅	n ₆	n ₅₊ n ₆
Negative	n ₃	n ₄	n ₃₊ n ₄	n ₇	n ₈	n ₇₊ n ₈
	n ₁₊ n ₃	n ₂₊ n ₄	N _{R-}	n ₅₊ n ₇	n ₆₊ n ₈	N _{R+}

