The studies estimating the relapse rate of patients after discontinuation of imatinib are still limited in number, based on a relatively low number of patients, heterogeneous by time on treatment, observation time accrued after discontinuation and therapy preceding imatinib (39, 40, 41). According to the preliminary results of the STIM study (40) that included patients in CMR for at least 24 months, 42 out of 69 patients followed for 13-30 months (median 24 months) since imatinib discontinuation relapsed. Thirty-nine percent (95% CI 28-51%) of patients were still negative at Q-RT-PCR performed at repeated occasions after discontinuation. Due to the lack of robust estimates, the sample size has been calculated assuming that $NPV_{Q-RT-PCR}$ equals to the lower limit of the 95% CI of the relapse free rate reported above i.e. 28%. If true rate of $NPV_{Q-RT-PCR}$ is higher the sample will provide the test with more power. Also, according to a pilot experience conducted within ILTE protocol, only 1/3 of patients negative by Q-RT-PCR are also negative by dPCR. Finally, n₃ and n₇ were assumed to be 0 because, being the dPCR method more sensitive than Q-RT-PCR, it is highly unlikely that the former turns to be negative when actually the latter is positive. With $\alpha=0.05$, $\beta=0.20$, $\delta=\gamma=1.5$ under the alternative hypothesis and the above assumptions the sample size required calculated according to reference (42) is 98 patients.

Definition of Analyzed Study Populations

All enrolled patients will be evaluated. Patients who withdraw or die before 36 months from the day 1 of the study will be considered as not evaluable.

Analyses

The data will be analyzed by Milano International Oncology or designee. rNPV will be calculated as the ratio of the Predicted Negative Values by the two tests respectively. If the lower 95% confidence limit will be greater than 1.5 one would conclude that the new method is more effective in predicting negative value as compared to the traditional one.

Progression free survival computed as the day since enrolment to the day of relapse or death will be analyzed by Kaplan-Maier method. The sensitivity and specificity of dPCR to predict molecular relapse will be assessed, as well as the overall and progression free survival of patients.

Promoter: University Milano-Bicocca

Product: Imatinib

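### The not-evaluable rule removes patients whose relapse is already declared, so known primary outcomes are discarded and the NPVs can be biased in either direction

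*Protocol*

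**What the plan says.** The protocol's section Definition of Analyzed Study Populations has two sentences: "All enrolled patients will be evaluated", then "Patients who withdraw or die before 36 months from the day 1 of the study will be considered as not evaluable". Neither says which analysis it applies to.

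The primary endpoint is the "Negative Predicted Rate (NPV) of dPCR, i.e. the capability of the method to predict relapse-free patients". The table under Sample size has two outcome classes, relapse-free at 3 years and "Relapsed within 3 years since discontinuation". Study Design and Methods defines relapse: "in case of results confirmation and at least one BCR/ABL / BCR value >0.1%, the loss of the molecular remission will be declared". This can happen at any point in follow-up.

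Relapse does not end participation. Patients resume imatinib and are still assessed for progression and resistance, with quality of life collected "for relapsing patient at months 1, 6, 12 after imatinib resumption". On overall follow-up the same section says that "each center will collect the data for 36 months".

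Under Analyses, death is an event: "Progression free survival computed as the day since enrolment to the day of relapse or death". Overall survival is also planned there.

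**The concern.** Whether a patient is evaluable depends on what happens up to month 36, but the primary outcome may be known long before. A patient whose relapse is declared at month 4 and who withdraws or dies at month 20 has a known class in the NPV table. Read literally, the rule removes that patient. The most serious case is a dPCR-negative patient who relapses, progresses and dies before month 36. This is the worst false negative the study could record, and it would leave both the NPV and, if the rule is general, the secondary endpoint on progression and resistance. A patient followed relapse-free to month 34 is dropped too, although almost all the information has been collected.

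The rule also fits badly with a progression-free survival in which death is an event, and with overall survival, which cannot be estimated properly if those who die are left out.

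The NPV of dPCR is meant to support a policy for stopping imatinib, and it rests on few patients. With 98 enrolled and one third dPCR-negative, about 33 patients and 19 relapses determine it, so a few deletions matter.

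**Working it through.** **Inputs (Protocol, Sample size).** NPV of Q-RT-PCR 0.28; one third of patients dPCR-negative (π = 1/3); target ratio 1.5, hence NPV of dPCR 0.28 × 1.5 = 0.42; n3 = n7 = 0; α = 0.05; power 80%; N = 98. Withdrawal and death rates are not given, so all loss rates below are assumptions.

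**Reproducing 98.** For paired predictive values with every patient Q-RT-PCR negative, the delta method gives

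N·Var(ln rNPV) = (1−NPVd)/(π·NPVd) + (1−NPVq)/NPVq − 2(1−NPVd)/NPVq = 0.58/0.14 + 0.72/0.28 − 2(0.58)/0.28 = 4.143 + 2.571 − 4.143 = 2.571.

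With null rNPV = 1 and one-sided 5%: N = (1.645 + 0.842)² × 2.571 / (ln 1.5)² = 96.7, so 97, close to the stated 98. Two-sided 5% gives 123. The power figures below use the setting that reproduces 98.

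**Expected cells as shares of the cohort.**
- dPCR-negative: relapse-free 0.42/3 = 0.140; relapsed 0.58/3 = 0.193.
- dPCR-positive: relapse-free 0.28 − 0.140 = 0.140; relapsed 0.72 − 0.193 = 0.527.

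**Effect of the rule.** Let f be the share of relapse-free patients removed, and r₋ and r₊ the shares of relapsed dPCR-negative and dPCR-positive patients removed. Then

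NPVd = 0.140(1−f) / [0.140(1−f) + 0.193(1−r₋)]

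NPVq = 0.280(1−f) / [0.280(1−f) + 0.193(1−r₋) + 0.527(1−r₊)]

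| Assumed loss | NPVd | NPVq | rNPV |
|---|---|---|---|
| None | 0.420 | 0.280 | 1.50 |
| 10% or 20% in every cell | 0.420 | 0.280 | 1.50 |
| Relapsed 10%, relapse-free 0% | 0.446 | 0.302 | 1.48 |
| Relapsed 20%, relapse-free 10% | 0.449 | 0.304 | 1.48 |
| Relapsed 5%, relapse-free 10% | 0.407 | 0.269 | 1.51 |
| Relapsed dPCR-negative 20%, all others 10% | 0.449 | 0.286 | 1.57 |
| Relapsed dPCR-positive 20%, all others 10% | 0.420 | 0.297 | 1.41 |

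For the third row: 0.140/(0.140 + 0.174) = 0.446; 0.280/(0.280 + 0.648) = 0.302; ratio 1.48.

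**How many known relapses go.** This was simulated with assumed exponential relapse times (mean 6 months) and 10% withdrawal over 36 months unrelated to relapse. About 6 observed relapses per 98 patients are deleted, with no bias in the NPVs. If the withdrawal hazard doubles after relapse, about 11 are deleted and the results are 0.442, 0.298 and 1.48. If it halves, about 3 are deleted and the results are 0.409, 0.271 and 1.51.

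**A half-fix fails.** In the same simulation with 10% unrelated withdrawal, restoring observed relapses while still dropping relapse-free withdrawals gives 0.399 and 0.262, below the true 0.42 and 0.28.

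**Power.** With 10% loss, 98 × 0.9 ≈ 88 remain. ln 1.5/√(2.571/88) − 1.645 = 0.727, a power of 0.766, against 0.805 at 98. The sample size text mentions no allowance for this. Keeping 98 evaluable would need 98/0.9, so 109 enrolled.

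**The case against.** Four objections deserve an answer.

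- **Direction of bias.** A reader might infer that the rule inflates the NPVs, because relapsed patients back on treatment have less reason to stay. The documents do not establish this. Relapsed patients remain under assessment, and completing a shorter schedule is not withdrawal. Equal loss changes nothing, and heavier loss among relapse-free patients reverses the sign. This objection stands, and only a possible bias in either direction is claimed here. Equal loss is not supported either. Relapse-free patients have quality-of-life assessments to month 36, a final dPCR sample and two further years of follow-up, whereas assessments after relapse are listed only to 12 months after resumption.
- **Contradiction.** A reader might also see a flat contradiction between the two population sentences. The second can be read as an exception to the first, so that reading is weak. Similarly, calling a death without relapse not evaluable for a binary relapse outcome is not in itself inconsistent with a composite survival endpoint. What stands is that the scope of the rule is unstated.
- **Size.** When loss does not depend on dPCR status, the ratio moves little, and the wider 1.41 to 1.57 needs differential loss that nothing in the text suggests. The power loss is small too. At the 39% point estimate in the sample size text, the same formula gives about 94% at 98 patients and 92% at 88. Both points are fair.
- **SAP.** Estimator details belong in a SAP, which was not available for this review. But the exclusion itself is fixed in the protocol, and it is wrong as written.

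**Conclusion.** The point holds in a limited form. From the text alone, and with no assumption, the rule discards primary outcomes that the protocol's own table has already classified. It also discards usable follow-up from relapse-free withdrawals, and it leaves unclear how deaths enter the other analyses.

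Bias is possible but not shown, and neither its direction nor its size can be fixed from the documents. In the worked examples, under assumed loss rates, the dPCR NPV lies between 0.407 and 0.449 against 0.42. The ratio lies between 1.48 and 1.51 if loss does not depend on dPCR status, and between 1.41 and 1.57 if it does. The fall in power from about 80% to 77% rests on an assumed 10% loss and on a null ratio of 1 at one-sided 5%. That setting reproduces 98 but is not the null hypothesis the protocol writes, which is a separate matter.

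**What to change.** 1. Count every relapse declared within 36 months of discontinuation as relapsed, whatever happens to the patient afterwards.
2. Do not simply add these patients back while still dropping relapse-free withdrawals. Estimate the 36-month relapse-free proportion, overall and by dPCR group, with withdrawals censored, and give rNPV a matching interval, for example by bootstrap.
3. State one rule for death without relapse in the NPV analysis and report the alternative as a sensitivity analysis. The choice matters: treating such a death as a competing event and taking 1 minus the cumulative incidence of relapse leaves the patient counted as relapse-free, whereas progression-free survival counts the same death as a failure.
4. Keep the complete-case table as a sensitivity analysis only. State that the not-evaluable rule does not apply to progression-free survival, overall survival or the progression and resistance endpoint.

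The cost is protocol wording and slightly more analysis. No new data are needed, because the number and time of relapses are already among the variables to be monitored.

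### The 98 patients are an evaluable count with no allowance for loss, yet the protocol drops all who withdraw or die before month 36; at the planning values a 10% loss costs about 4 points of power

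*Protocol*

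**What the plan says.** The Sample size section of the protocol sets the aim: "Sample size will be calculated so to provide with 80% power". It plans on an NPV of 28% for Q-RT-PCR, a ratio of 1.5, and one third of Q-RT-PCR-negative patients being dPCR-negative. It ends with a single number: "the sample size required calculated according to reference (42) is 98 patients". It gives no expected loss rate, no inflation and no separate enrolment target.

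Definition of Analyzed Study Populations follows directly and has two sentences. The first says that every enrolled patient is to be assessed. The second says "Patients who withdraw or die before 36 months from the day 1 of the study will be considered as not evaluable".

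The 28% is a deliberate choice. The source estimate is "Thirty-nine percent (95% CI 28-51%) of patients were still negative at Q-RT-PCR", and the protocol takes its lower limit, noting that a higher true rate would give more power.

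**The concern.** The primary endpoint needs each patient's relapse status over three years. If 98 is the number of known outcomes that the formula requires, and the protocol also removes everyone who leaves or dies during those three years, the number enrolled and the number analysed are different quantities. The protocol gives one figure for both.

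Two things are at stake. One is power: enrolling 98 would give fewer than 98 analysable patients as soon as anyone is lost. The other is the content of the rule. As worded, it depends only on whether the patient left or died before month 36, not on whether relapse had already been seen. A patient who relapsed at month 4 and withdrew at month 20 has a known outcome but would be dropped.

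**Working it through.** **Inputs (Sample size section).** NPV of Q-RT-PCR = 0.28; ratio under the alternative γ = 1.5, so NPV of dPCR = 0.42; share dPCR-negative q = 1/3; α = 0.05; power 80%; n₃ = n₇ = 0. All patients enter Q-RT-PCR-negative, so n₁ and n₅ are also zero.

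**Cell probabilities.** p₄ = 0.42 × 1/3 = 0.140; p₈ = 1/3 − 0.140 = 0.193; p₂ = 0.28 − 0.140 = 0.140; p₆ = 1 − 0.473 = 0.527.

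**Variance of log rNPV per patient (delta method).** log rNPV = log p₄ − log(p₄ + p₈) − log(p₂ + p₄). The derivatives are:
- g₄ = 1/0.14 − 3 − 1/0.28 = 0.571
- g₈ = −3
- g₂ = −1/0.28 = −3.571
- g₆ = 0

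Σpg² = 0.046 + 1.740 + 1.786 = 3.571. Σpg = 0.08 − 0.58 − 0.50 = −1. So V = 3.571 − 1 = 2.571.

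**Reproducing 98.** N = (z_α + z_β)² × V / [ln(γ/δ)]².
- One-sided 5%, δ = 1: 6.183 × 2.571 / 0.1644 = 96.7; with 0.33 in place of 1/3, 98.3. This matches 98 to within rounding of the share.
- Two-sided 5%, δ = 1: 122.8 (124.8 with 0.33). No match.
- δ = γ = 1.5 as printed: ln(γ/δ) = 0, so no finite N exists.

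So 98 is the bare formula result for patients with a known outcome.

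**Power if 98 are enrolled.** Power = Φ(ln 1.5 × √(n/2.571) − 1.645). The loss rates are assumptions.

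| Assumed loss | Evaluable | Power |
|---|---|---|
| 0% | 98 | 80.5% |
| 2% | 96 | 79.7% |
| 5% | 93 | 78.6% |
| 10% | 88 | 76.6% |
| 15% | 83 | 74.5% |
| 20% | 78 | 72.2% |

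A simulation of the Wald test on log rNPV gives a lower level but losses of similar size: 75.4% at 98, 72.0% at 88 and 67.5% at 78. The differences in the table are therefore more dependable than its absolute values.

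**If the true NPV is above 28%** (ratio 1.5 and share 1/3 kept). At 30%, V = 2.333 and 88 evaluable give 80.1%. At 33%, 78 give 80.7%. At 39%, 78 give 88.8%.

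**Effect of discarding observed relapses.** Suppose, for illustration, that 10% of relapsed patients later leave and are dropped, and no relapse-free patient leaves.
- Whole cohort: 0.28 / (0.28 + 0.72 × 0.9) = 0.302 instead of 0.28.
- dPCR-negative: 0.42 / (0.42 + 0.58 × 0.9) = 0.446 instead of 0.42.
- Ratio: 0.446 / 0.302 = 1.48 instead of 1.50.

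Both NPVs rise. If leaving were unrelated to relapse, dropping these patients would cost numbers but not bias the NPVs.

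**The case against.** The strongest reply is that the plan is already conservative. It uses the lower confidence limit of a 39% estimate and says that a higher true rate adds power. That is correct: at 39%, about 59 evaluable patients suffice, and 80% power survives a loss of roughly 40%. What does not stand is treating this as an attrition allowance. The protocol justifies 28% by the lack of robust estimates, so the cushion is for uncertainty in the NPV. If 28% is right, nothing is left over for loss.

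It is also fair that 98 is called a required size and that nothing says enrolment stops there. The protocol gives only an entry window and an approximate number of centres, so one cannot conclude that fewer than 98 will be analysed. What can be said is that no enrolment target or loss allowance is stated.

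Three stronger readings are tempting and not supported.
- **That 80% holds provided nobody is lost.** With δ = γ = 1.5 and a decision rule requiring the lower limit to exceed 1.5, power at a true ratio of 1.5 is Φ(−1.645) = 5%, or 2.5% with a two-sided 95% limit, even with complete follow-up.
- **That loss takes power into the 60s.** With the lower end of a two-sided 95% interval and a null ratio of 1, power is 68.4, 66.0, 63.4 and 60.8% at 5 to 20% loss, but it is already 70.6% with none. About 10 points come from the change of critical value, and 5% loss costs about 2.
- **That dropping relapsed leavers favours dPCR.** The documents do not settle the direction for the ratio. In the illustration above it moves slightly towards 1.

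**Conclusion.** The concern holds in a limited form. There is no arithmetic error: 98 reproduces. The fault is that it reproduces only as a count of known 36-month outcomes, while the protocol fixes an exclusion rule that separates enrolled from evaluable patients and makes no allowance for the difference. At the planning values, the second lost patient takes power below 80%. A 10% loss from 98 costs about 4 points and a 20% loss about 8.

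These figures rest on a null ratio of 1, a one-sided 5% test, an NPV of 28%, a share of 1/3 and assumed loss rates. The point is secondary to the δ = γ = 1.5 defect, which has to be settled before any power statement means anything; settling it does not remove this one.

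The two sentences on the analysed population contradict each other. Read literally, the second also throws away known relapses. That biases the NPVs upward if patients leave more often after relapse than while relapse-free.

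**What to change.** 1. State that 98 is the number of evaluable patients, give an assumed loss rate, and restate the power for the evaluable number expected from 98 enrolled (for example about 77% at an assumed 10% loss, with null ratio 1). A sponsor who prefers to keep 80% at the planning values would enrol 98 / 0.9, that is 109, at the same assumed loss; the fix does not depend on this.
2. Reconcile the two sentences in Definition of Analyzed Study Populations.
3. Count every observed relapse, whatever happens to the patient afterwards.
4. Estimate the 36-month relapse-free rate in the dPCR-negative group and in the whole cohort by Kaplan-Meier, with withdrawals censored, and form rNPV from these. State how death without relapse is handled: the Kaplan-Meier analysis already planned for progression-free survival counts death as an event, so its definition does not simply carry over. Use a variance for the ratio that allows for the overlap, since the dPCR-negative group is part of the cohort.

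Steps 3 and 4 belong together. Keeping observed relapses while still dropping patients who withdraw relapse-free would push the NPVs downward.

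The cost is a slightly less favourable stated power and an assumption that withdrawal is non-informative. How much of the lost power the Kaplan-Meier estimate recovers has not been calculated. No additional patients are required.

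### The null margin, the assumed ratio and the success threshold for rNPV are all 1.5, so at the planning values the stated rule has about 2.5–5% power, not 80%

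*Protocol*

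**What the plan says.** All of this is in the protocol synopsis.

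- **Sample size, aim.** "Sample size will be calculated so to provide with 80% power the alternative hypothesis" that the NPV of dPCR "will exceed the one of traditional Q-RT-PCR, by more than 1.5". The formal null is rNPV at or below delta and the alternative is rNPV above delta, so the 1.5 is a ratio.
- **Sample size, inputs.** The NPV of Q-RT-PCR "equals to the lower limit of the 95% CI of the relapse free rate reported above i.e. 28" per cent. On the dPCR-negative share, "only 1/3 of patients negative by Q-RT-PCR are also negative by dPCR". The cells n3 and n7 are taken as zero. Alpha is 0.05 with no sidedness given, beta is 0.20, and delta and gamma are both 1.5.
- **Sample size, result.** "under the alternative hypothesis and the above assumptions the sample size required calculated according to reference (42) is 98 patients".
- **Analyses, decision rule.** "If the lower 95% confidence limit will be greater than 1.5 one would conclude that the new method is more effective".

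The Sample size section adds that a true NPV of Q-RT-PCR above 28% would increase power.

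**The concern.** Power is the chance of rejecting the null when the truth lies some distance inside the alternative. Here the null extends up to 1.5, and the only ratio given for the alternative is also 1.5, so that distance is zero. A test evaluated on its own null boundary rejects at its type I error rate, whatever the sample size.

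This is the success criterion for the primary endpoint. If dPCR performed exactly as planned, raising the NPV from 28% to 42%, the trial would fail its own rule about 95% of the time or more, and an assay that met expectations would be reported as not shown to be better. The 80% in the protocol describes some other test from the one that would be carried out.

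**Working it through.** **Inputs.** Q = NPV of Q-RT-PCR = 0.28; D = NPV of dPCR = 1.5 × 0.28 = 0.42; p = share of patients negative by dPCR = 1/3; N = 98; n3 = n7 = 0. All are from the Sample size section. Entry requires negative Q-RT-PCR, so every patient counts in Q. D is taken as n4/(n4 + n8), the relapse-free share of the dPCR-negative row. The printed formula shows n6 + n8 in the dPCR denominator, which does not match the table. Reference (42) is not available, so a standard large-sample formula for the log of a paired ratio is used.

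**Variance.** N × Var(log rNPV) = (1−D)/(pD) + (1−Q)/Q − 2(1−D)/Q
= 4.143 + 2.571 − 4.143 = 2.571 (2.613 if 1/3 is entered as 0.33).
The standard error at N = 98 is √(2.571/98) = 0.162.

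**Step 1: reproduce 98.** N = (z_alpha + z_beta)² × 2.571 / [ln(true ratio / null ratio)]².

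- Null 1, truth 1.5, one-sided 5%: (1.645 + 0.842)² × 2.571 / 0.4055² = 96.7, so 97. With share 0.33 it is 98.3, so 99. The stated 98 lies between.
- Null 1, truth 1.5, two-sided 5%: 122.8 (124.8 with share 0.33).
- Null 1.5, truth 1.5, as written: ln(1.5/1.5) = 0, so no finite N exists.
- Other forms at one-sided and two-sided 5%: log ratio ignoring the pairing, 253 and 321; difference scale, 141 and 179; dPCR-negative against dPCR-positive patients as two proportions, 132 and 168; null 1.5 with truth 2.25, 64 and 81. None gives 98.

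**Step 2: power of the written rule at N = 98 and true ratio 1.5.** Power = Φ(ln(1.5/1.5)/0.162 − z_alpha) = Φ(−z_alpha).

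| Lower limit used | Formula | Simulated (1,000,000 trials, Wald interval on log rNPV) |
|---|---|---|
| One-sided 95% | 5.0% | 5.9% |
| Two-sided 95% | 2.5% | 3.2% |

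**Step 3: observed ratio needed.** The limit is computed from the observed data, and the standard error falls as the ratio rises. Solve ln(r/1.5) = z_alpha × SE(r), with Q = 0.28, p = 1/3 and N = 98. This gives r = 1.88 (one-sided) or 1.96 (two-sided).

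**Step 4: true ratio at which 98 patients give 80% against 1.5.** Solve ln(r/1.5) = (z_alpha + 0.842) × SE(r).

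- One-sided: r = 2.09, SE 0.133, dPCR NPV 2.09 × 0.28 = 58%.
- Two-sided: r = 2.17, SE 0.132, dPCR NPV 2.17 × 0.28 = 61%.

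Between these points, one-sided and two-sided power is 28% and 19% at a true ratio of 1.75, and 69% and 57% at 2.0.

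**Step 5: power against a null of 1 at N = 98 and true ratio 1.5.**

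| Lower limit used | Formula | Simulated |
|---|---|---|
| One-sided 95% | Φ(0.4055/0.162 − 1.645) = 80% | 75% |
| Two-sided 95% | Φ(0.4055/0.162 − 1.960) = 71% | 67% |

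**Step 6: the remark about a higher NPV of Q-RT-PCR.** With Q = 0.39 and a true ratio of 1.5, one-sided power against 1 rises to 94%. Under the written rule it stays at 5% (one-sided) or 2.5% (two-sided), so the remark fits a null of 1 but not the stated rule.

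**The case against.** The strongest defence is that the cited method is not at hand and the protocol never defines gamma. Reading gamma as the assumed true ratio is an inference. That much stands, but it does not rescue the plan: whatever gamma denotes, no ratio above 1.5 is stated, and none of the protocol's figures supports 80% power for a lower limit above 1.5.

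Three stronger readings are tempting and go too far.

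- **That 98 can come only from a test against 1.** The formula gives 97 or 99, not exactly 98, and a true ratio near 2.1 tested one-sided against 1.5 also needs about 95 to 98 patients. The test against 1 is the most plausible source because it uses the stated 1.5; it is not proven.
- **That the trial is bound to fail.** The 2.5–5% applies at the planning value. If the true ratio were 2.0, power would be 57% to 69%.
- **That moving the threshold to 1 secures 80% at no cost.** The 80% is a large-sample figure; simulation gives about 75%. It also needs all 98 patients to be evaluable. The Definition of Analyzed Study Populations section makes withdrawals and deaths before 36 months not evaluable, and no inflation is stated. With 10% lost (an assumption, leaving 88), one-sided power is 77% by formula and 72% by simulation.

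It can also be said that the wording of the aim, the hypotheses and the decision rule all agree on a 1.5 margin, so it may be intended. If so, the power statement is what must change.

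**Conclusion.** The point holds. The hypotheses and the decision rule use 1.5 as the bar to clear, and the sample size calculation offers nothing above 1.5 as the truth. At NPVs of 28% and 42%, a dPCR-negative share of 1/3 and 98 evaluable patients, the rule has about 5% power (one-sided limit) or 2.5% (two-sided interval) in place of the stated 80%. The contradiction itself does not depend on the variance formula or the cited method, because on the null boundary power equals the type I error for any valid test.

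The attribution of 98 to a test against 1 is less certain and rests on an approximate match under a standard formula. The other figures assume a log-scale Wald interval and would shift somewhat with another interval method. Since this is the primary success criterion, it must be corrected.

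**What to change.** Make the hypotheses, the decision rule and the power statement describe one test, and say whether the 95% limit is one-sided or two-sided. Either option serves.

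- **(a) Test against 1.** State the null as rNPV at or below 1, with 1.5 as the planning value, and declare success if the one-sided 95% lower limit exceeds 1. State power with 98 evaluable patients as about 80% by the asymptotic formula and about 75% by simulation with a Wald log interval; with a two-sided 95% interval, about 71% and 67%. The cost is a weaker claim: dPCR predicts better than Q-RT-PCR, not more than 1.5 times better. If 80% is wanted in simulation, about 115 to 120 evaluable patients are needed one-sided and slightly over 140 two-sided.
- **(b) Keep the 1.5 margin.** State that 98 evaluable patients give about 80% power only if the true rNPV is about 2.1 (one-sided) or 2.2 (two-sided), a dPCR NPV of about 58% to 61%. Justify that value, or state another above 1.5 and recalculate N. The cost is either a more demanding assumption or a larger trial: at a true ratio of 2.0, the formula needs about 134 patients one-sided or 170 two-sided.

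In both cases, say how non-evaluable patients are allowed for. Under (b), also drop or qualify the remark that a higher NPV of Q-RT-PCR adds power, since it does not when the true ratio equals the margin.
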